3.3 Subject Withdrawal Criteria

Subjects may be removed from the study for reasons including the following:

1. Intolerance to a required study procedure at any time point.
2. Noncompliance with protocol restrictions and requirements (e.g., failure to remain at the test facility for the duration of the evaluation period) at any time point.
3. The occurrence of a serious adverse experience at any time point.
4. Subject withdrawal of consent at any time point.
5. Investigator considers it advisable or in the subject's best interest.

4 STUDY TREATMENTS

4.1 Identity of Test Products

The following test products will be used on this study. Test product Code A will be provided by the Sponsor. Test product Code B (negative control) will be provided by Princeton Consumer Research.

Princeton Code	Sponsor Code	Patch Type	Concentration	Method and Quantity of Application to Patch
A	[REDACTED]	Occlusive	Neat	Quantity sufficient to saturate the Webril patch pad ~0.2 mL squeezed out from the 2.5 mL squeeze vial
B	0.9% aqueous sodium chloride	Occlusive	Neat	0.2 ml via Pipette onto Webril patch pad

Both PCR Codes A and B will be placed onto the patch pads at the quantities listed above. These patch pads will be adhered to the application sites located on the back and marked with a skin marker. Additional adhesive tape may be used to ensure patch contact with the skin.

4.2 Test Product Storage and Accountability

Upon receipt, the test products will be inventoried and stored at room temperature (about 15-30°C).

Physiological saline (0.9% Aqueous Sodium Chloride) will serve as a negative control.

Both products will be placed on patches no more than 30 minutes before application.

All application and removal of test materials will be recorded for each subject.

All unused test products (excluding the negative control) will be returned to or destroyed following Sponsor instruction after completion of the study.

4.3 Methods of Assigning Subjects to Treatment Groups

At the testing facility, a unique 3-digit screening number will be assigned to each subject after written Informed Consent is obtained. Subject screening numbers will be assigned sequentially at the testing facility. Princeton Consumer Research will develop the randomization scheme. At Visit 2, a 2-digit randomization number will be assigned by Princeton Consumer Research to each subject in a sequential manner as they become eligible for randomization. To eliminate any position bias, the assignment of the test product codes to the test sites will be randomized among the subjects so that each test product code occupies individual skin sites within panel of test subjects with equal frequency. The randomization number will correspond to a predetermined assignment design. Randomization numbers must not be re-used once assigned, even if the subject is not administered the test products. There will be no replacement of subjects who are withdrawn prior to completion of the study.

4.4 Administration of Test Products

For all subjects, the test products will be placed, on Webril patch pads (2 x 2 cm) adhered to occlusive tape (approximately 4 x 4 cm) and will be applied as per study design and randomization scheme onto designated sites located on the back of each subject unless the skin condition becomes sufficiently irritated to require a change to a semi-occlusive tape or even an open dressing, at the discretion of the investigator.

The patches will be reinforced with additional non-irritating tape as deemed necessary by the patch applicator. Subjects will be instructed to keep all patches dry during showering so that the test sites are protected from accidental water exposure for the duration of the study.

Two test sites located on one side of the paraspinal region of the back will be utilized for application. The assignment of the test product codes to individual skin sites will be randomized so that each test product code occupies individual skin sites within the panel of test subjects, with approximately equal frequency, in order to eliminate any position bias. The sites of patch/test product application will be marked by a skin marker so that the location of the patch pad/application site is clearly indicated for evaluations.

The test products will be applied and removed by study personnel. The study will involve repetitive and continuous patch applications of all investigational products, Codes A and B, approximately 48 hours on weekdays and for approximately 72-hour periods over weekends over 3 weeks, for a total of 9 induction applications. All applications for individual test products will be made to the same site unless reactions become so strong as to make this inadvisable. If excessive irritation, (for example, a numerical score of 2 or greater) is noted, that site will be discontinued from further patching and a new site adjacent to the original site will be used for the remainder of the required applications (move site 1). If excessive irritation occurs at the move site, a second move site may be used. Excessive irritation at the second move site would require discontinuation of that patch. Residue on the skin from any test patch will be removed by study staff prior to skin evaluation (if observed) by gently wiping the patch application site with a moistened gauze pad.

Photos will be taken of any reactions of concern and will be shared with the sponsor but will not be part of the final report.

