3.2 Exclusion Criteria

1. Clinically significant skin disease which may contraindicate participation, including psoriasis, eczema, atopic dermatitis, and active cancer;
2. Asthma that requires medication;
3. Insulin-dependent diabetes;
4. Known immunological disorders such as HIV positive, AIDS and systemic lupus erythematosus;
5. Treatment for any type of cancer within the last six months;
6. Routine use (as defined by using more than 3 days in a week) of any anti-inflammatory drug (e.g., aspirin, ibuprofen, corticosteroids; 81 mg aspirin is acceptable), immunosuppressive drugs, antihistamine medication (steroid nose drops and/or eye drops are acceptable) or over-the-counter pain medication that is ingested in quantities exceeding label instructions;
7. Use of topical drugs at patch site;
8. Pregnancy, lactation, or planning a pregnancy (confirmed by a urine pregnancy test administered to females of childbearing potential);
9. Medical condition which, in the Investigator's judgement, makes the subject ineligible or places the subject at undue risk;
10. Participation in any patch test for irritation or sensitization within the last four weeks;
11. Dermatological aberrations in or around test sites which includes sunburn, extremely deep tans, uneven skin tones, tattoos, scars, excessive hair, numerous freckles, or any other disfigurement of the test site;
12. Confirmed allergy to adhesives, bandages, or ingredients in OmezaTM Collagen Matrix;
13. History of anaphylaxis to matrix ingredients (e.g. fish, palm oil, hemp oil, beeswax).

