4.6 Blinding and Unblinding Method

Study products will be administered in a single-blinded fashion, i.e., the treatment assignment will not be known to the skin evaluator.

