6.5 Patch Application and Removal

PCR staff will apply the patches according to the predetermined randomization schedule. Each test product will remain on the skin for approximately 48 hours on the week days and 72-hour periods over the weekend for the Induction phase of the study for a total of 9 induction applications. Application 1 will occur at Visit 1. At Visit 2 and every day of patch removal, there should be an approximate 15-minute waiting period to let any erythema from patch removal subside prior to the skin evaluation. All remaining patch applications will occur following the same randomization scheme as on Visit 1.

For the Challenge Phase of the study, patches will be applied once and be worn for approximately 48 hours. There will be an approximate 30-minute waiting period from patch removal prior to the first evaluation. Subsequent evaluations will take place 24 (± 1), 48 (± 2) and 72 (± 2) hours post challenge patch removal.

All patch preparation, application, removal, and evaluation times will be recorded on source documents.

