6.6 Skin Assessments and Procedures

All subjects will be evaluated using the Skin Irritation Scale:

Inflammatory Responses:

0	=	No visible reaction
+	=	Slight, confluent or patchy erythema
1	=	Mild erythema (pink)
2	=	Moderate erythema (definite redness)
3	=	Strong erythema (very intense redness)

Definition of letter grades appended to a numerical grade:

E	=	Edema - swelling, spongy feeling when palpated
P	=	Papule - red, solid, pinpoint elevation
V	=	Vesicle - small elevation containing fluid
B	=	Bulla reaction - fluid-filled lesion (blister)
S	=	Spreading - evidence of the reaction beyond the Webril pad area
W	=	Weeping - result of a vesicular or bulla reaction - serous exudate
I	=	Induration - solid, elevated, hardened, thickened skin

Superficial Effects

g	=	Glazing
y	=	Peeling
c	=	Scab, dried film of serous exudate of vesicular or bulla reaction
d	=	Hyperpigmentation (reddish-brown discoloration of test site)
h	=	Hypopigmentation (loss of visible pigmentation at test site)
f	=	Fissuring grooves in the superficial layers of the skin

All skin responses observed during the induction and challenge phases will be reported. Skin responses to each patch application will be examined and graded under light supplied by a 100-watt incandescent blue bulb. The evaluator and Investigator will be blinded to treatment assignment and any previous scores. The same individual will conduct all skin evaluations of the test sites, but a qualified back-up individual will be available if needed.

Individual investigational products during the induction phase will be applied to the assigned skin site unless the site reactions become so strong as to make it inadvisable. If excessive irritation, (for example, a numerical score of 2 or greater or any grade (even 0) if appended with a letter grade of E, P, V or B) is noted, that site will be discontinued from further patching and a new site adjacent to the original site will be used for the remainder of the required applications. If excessive irritation occurs at the move site, a second move site may be used. Excessive irritation at the second move site would require discontinuation of that patch material.

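### Residue is wiped before grading only where it is seen, so the product and saline sites can be handled differently just before a blinded erythema grade

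*Combined protocol and SAP*

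**What the plan says.** Section 4.4 gives the rule: "Residue on the skin from any test patch will be removed by study staff prior to skin evaluation (if observed"). The method is "by gently wiping the patch application site with a moistened gauze pad". The trigger is residue seen at a given site. The rule names neither product and says nothing about the site without residue.

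Section 6.5 puts an interval between patch removal and grading. In induction it is an "approximate 15-minute waiting period to let any erythema from patch removal subside prior to the skin evaluation". At challenge it is about 30 minutes. The visit lists in Sections 5.2, 5.3 and 5.6 give removal, wait and evaluation, with no wiping step.

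On blinding, Section 4.6 says "the treatment assignment will not be known to the skin evaluator", and Section 6.6 says "The evaluator and Investigator will be blinded to treatment assignment and any previous scores". Section 6.6 also has one person do all the grading, with a back-up available.

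On the two materials, Section 3.2 excludes "History of anaphylaxis to matrix ingredients (e.g. fish, palm oil, hemp oil, beeswax"). Section 4.1 describes the control as "0.2 ml via Pipette onto Webril patch pad", the liquid being 0.9% aqueous sodium chloride.

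**The concern.** In a within-subject comparison, the two sites should differ only in what was on the patch. A wipe triggered by visible residue breaks that whenever residue is commoner under one material. An oil and beeswax product is more likely to leave something visible than saline is.

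Two consequences are possible:

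- **Recognition.** A damp or freshly wiped site, or a wipe that the evaluator sees being done, points to the product. Each subject has two induction sites (Section 4.4), so identifying one identifies the other. Induction applications stay on the same sites unless irritation forces a move, and the same person normally grades throughout, so a single cue could carry over to later visits.
- **Redness from handling.** The grade is visual, with fine low steps (0, +, 1). Section 6.5 itself accepts that removing a patch can redden the skin, and allows time for this to fade. A wipe done after that time would have no such interval.

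This matters more than it would in a trial with a formal test. Section 7.2 plans tabulation only, and under Section 6.8 the conclusion comes from the graders' scores and the investigator's judgement. Equal handling and blinded grading are therefore among the main safeguards.

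**Working it through.** The plan states no figure on this point, so there is none to reproduce. The check has three parts.

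**1. Do other sections close the gaps in Section 4.4?**

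| Question | What the protocol gives |
|---|---|
| Who wipes? | Study staff (4.4); not stated whether this excludes the evaluator |
| When? | Before evaluation (4.4); not stated whether before or after the wait (4.4, 6.5, 5.2, 5.3, 5.6) |
| Which sites? | Any site with residue (4.4); no matching wipe of the other |
| Is the evaluator out of sight? | Not stated (4.4, 4.6, 6.6) |
| How often is residue left, and where? | Not stated |

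No section closes them. Following the rule as written can mean wiping one site and not the other shortly before both are graded.

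**2. Which readings are exposed?**

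- Gradings per site: 9 induction + 4 challenge (30 min, 24, 48 and 72 h) = 13.
- Gradings that follow a patch removal, and so possibly a wipe: 9 + 1 = 10.
- Gradings that follow no new removal: 13 − 10 = 3.
- Upper bound on exposed paired readings: 60 subjects × 10 = 600, or 50 completers × 10 = 500. These count opportunities for a wipe. They do not count affected readings.

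Direction under Section 6.8: sensitization is judged by a challenge reaction exceeding the induction reaction. Wiping redness that raised product scores in induction would make a challenge reaction look less enhanced. Wiping redness at the 30-minute challenge reading would act the other way, by adding to a product reaction that the control lacks. Knowledge of the site could bias a grade in either direction.

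A cue at the 30-minute reading would also identify those same challenge sites at 24, 48 and 72 h. Recognition can therefore reach readings that wiping redness cannot.

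**3. How fast could occasional cues add up?**

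Let q be the chance that the evaluator gets a cue to the product site at one removal. The documents give no value, so q is assumed, and removals are treated as independent. The chance of at least one cue in k removals is 1 − (1 − q)^k.

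| Assumed q | k = 9 (induction) | k = 10 (all removals) |
|---|---|---|
| 0.02 | 1 − 0.98^9 = 17% | 1 − 0.98^10 = 18% |
| 0.05 | 1 − 0.95^9 = 37% | 1 − 0.95^10 = 40% |
| 0.10 | 1 − 0.90^9 = 61% | 1 − 0.90^10 = 65% |
| 0.20 | 1 − 0.80^9 = 87% | 1 − 0.80^10 = 89% |

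The table shows only that a small chance per removal accumulates over repeated removals in the same subject. If cues cluster in certain subjects, the chance at a given average q is lower than shown. It is not an estimate for this trial.

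**The case against.** The strongest reply is that one-sided residue is inferred, not documented. The rule covers any test patch. Both sites carry the same pads and tape, so residue need not come only from the product. The oils and beeswax appear as examples in an exclusion criterion, not in a description of the formulation, and Section 2.1 calls the product a liquid. This stands as far as it goes: a reader might infer that only the product site will be wiped, and the documents do not establish that. What remains is a reasonable expectation that the two sites will differ.

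Second, the rule also protects blinding. Product left on the skin would itself be a cue, and study staff remove it before grading. This stands, and it is a reason to keep wiping and make it symmetric, not to drop it.

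Third, the visit order of removal, wait and evaluation fits wiping as part of removal, in which case redness would have time to settle. That is a fair reading, but the text does not require it.

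Fourth, the reach is limited. The later challenge readings follow no new removal. Section 6.8 also describes a sensitization reaction as erythematous and edematous, often spreading past the patch, and nothing suggests that a gentle wipe produces edema or spread. This stands for direct wiping effects. It does not answer the risk of recognition.

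Last, wiping clean skin adds handling in an irritation test. That is a real cost, but it would be equal at both sites and followed by the wait.

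**Conclusion.** The point holds as a minor design weakness that is cheap to correct. Section 4.4 permits unequal handling of the two sites just before a blinded grade, and no other section prevents it.

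A reader might go further and conclude that blinding is lost, or that product scores are biased. The documents do not support either. Loss of blinding would require residue to occur mainly at one site, the wipe to be witnessed or still visible at grading, and the evaluator to draw the inference. None of these is documented. The size of any shift in erythema scores cannot be derived, and its direction differs between the induction readings and the 30-minute challenge reading.

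Direct exposure is at most 10 of 13 scheduled readings per site, and the 24, 48 and 72 h challenge readings lie outside it. The conclusion rests on one assumption from outside the text: that a product with oils and beeswax leaves visible residue more often than saline. No sample-size figure is affected.

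**What to change.** Replace the conditional rule in Section 4.4 with an unconditional one. At every patch removal, study staff who do not grade gently wipe both sites in the same way with moistened gauze, whether or not residue is seen. They do this immediately after removal, before the 15- or 30-minute wait starts, and out of the evaluator's view. Add the step between removal and wait in the visit lists of Sections 5.2, 5.3 and 5.6. The wipe can be noted with the removal times that Section 6.5 already has recorded. Any note of which site had residue should be kept from the evaluator.

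The cost is a short protocol change, one extra gauze pad per removal where only one site would have been wiped, and slight additional handling of residue-free skin. That handling is the same at both sites and is followed by the existing wait. No visit is added. The change removes the difference in wiping whatever the true residue rate.

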4.5 Treatment Accountability and Compliance

Since all test products are to be administered in-clinic, 100% compliance is anticipated. Subjects are required to attend all visits.

4.6 Blinding and Unblinding Method

Study products will be administered in a single-blinded fashion, i.e., the treatment assignment will not be known to the skin evaluator.

5 SCHEDULE OF PROCEDURES AND ASSESSMENTS

Table 6-1 represents the schedule of procedures and assessments at each of the scheduled visits. Details of each visit are provided in Sections 6.1 through 6.4.

Table 5-1 SCHEDULE OF PROCEDURES AND ASSESSMENTS

Period	Baseline	Induction Phase												Rest Phase	Challenge Phase				
		1	3	5	8	10	12	15	17	19	22		36	38	39	40	41		
Day																			
Visit	1	2	3	4	5	6	7	8	9	10				11	12	13	14	15	
Informed Consent/HIPAA	X																		
Demographics	X																		
Back check for excessive hair, moles, tattoos, dermatological conditions	X																		
Inclusion/Exclusion Criteria review	X																		
Urine Pregnancy Test	X																		
Patch Application	X	X	X	X	X	X	X	X	X	X				X					
AE/Con Med Review		X	X	X	X	X	X	X	X	X	X				X	X	X	X	
Patch Removal		X	X	X	X	X	X	X	X	X	X				X				
15 Minute Minimal Wait		X	X	X	X	X	X	X	X	X	X				X				
Irritation Evaluation		X	X	X	X	X	X	X	X	X	X				X ¹	X	X	X	

¹Evaluations to occur approximately 30 minutes after patch removal and 24 (± 1), 48 (± 2) and 72 (± 2) hours post challenge patch removal.

5.1 Qualifying Visit – First Application (Visit 1)

- Written Informed Consent
- Medical history
- Current medications (past 30 days)
- Brief dermal skin examination of the back
- Pregnancy Status confirmed by urine pregnancy test if applicable
- Eligibility review of Inclusion/Exclusion criteria
- Mark test sites/patch application

5.2 Induction Phase (Visits 2 – 9)

- Adverse event, concomitant medication review
- Patch removal
- Note: Approximate 15-minute wait time from removal to evaluation
- Skin Evaluation
- Mark test sites/patch application
- Photograph(s) if applicable

5.3 Induction Phase (Visit 10)

- Adverse event, concomitant medication review
- Patch removal
- Note: Approximate 15-minute wait time from removal to evaluation
- Skin evaluation
- Photograph(s) of sites if applicable

5.4 Rest Phase

- Subjects will have a rest period of 10-17 days

5.5 Challenge Phase (Visit 11)

- Adverse event, concomitant medication review
- Eligibility review
- Patch application

5.6 Challenge Phase (Visit 12)

- Adverse event, concomitant medication review
- Patch removal
- Note: Approximate 30-minute wait time from removal to evaluation
- Skin evaluation
- Photograph(s) of sites if applicable

5.7 Challenge Phase (Visit 13-15)

- Adverse event, concomitant medication review
- Skin evaluation
- Photograph(s) of sites if applicable

5.8 Protocol Deviations

This study is intended to be conducted as described in this protocol. In the event of a significant deviation from the protocol due to an emergency, accident, or mistake, the Principal Investigator must determine whether the subject should continue in the study.

6 DETAILED DESCRIPTION OF ASSESSMENTS

6.1 Informed Consent

Written Informed Consent will be obtained from each subject before any study procedures are performed. All potentially eligible subjects for the study will be given a copy of the informed consent form to read. The protocol will be discussed in detail with each potentially eligible subject. The study subject must sign the Informed Consent form if he/she decides to participate in the study. No study procedures will be performed, or study products applied to any subject who has not signed the Informed Consent form.

6.2 Eligibility Review

Princeton Consumer Research (PCR) staff under the oversight of the Principal Investigator reviews eligibility criteria at Visit 1. Each subject's eligibility will also be reviewed prior to randomization.

Screen Failure: A screen failure is defined as a subject who was consented but who was not randomized. Screen failures may not re-screen for the study.

6.3 Brief Examination of the Back

A brief dermal examination of the subject's back will be conducted by a trained associate and will consist of an evaluation of the dermal acceptability of the skin for patching after consent and preferably prior to moving to the interview. Exclusive conditions would include excessive hair, moles, tattoos, dermatological conditions, etc.

6.4 Pregnancy Tests

Urine pregnancy tests will be conducted at the testing facility on women of childbearing potential to confirm pregnancy status.

6.5 Patch Application and Removal

PCR staff will apply the patches according to the predetermined randomization schedule. Each test product will remain on the skin for approximately 48 hours on the week days and 72-hour periods over the weekend for the Induction phase of the study for a total of 9 induction applications. Application 1 will occur at Visit 1. At Visit 2 and every day of patch removal, there should be an approximate 15-minute waiting period to let any erythema from patch removal subside prior to the skin evaluation. All remaining patch applications will occur following the same randomization scheme as on Visit 1.

For the Challenge Phase of the study, patches will be applied once and be worn for approximately 48 hours. There will be an approximate 30-minute waiting period from patch removal prior to the first evaluation. Subsequent evaluations will take place 24 (± 1), 48 (± 2) and 72 (± 2) hours post challenge patch removal.

All patch preparation, application, removal, and evaluation times will be recorded on source documents.

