2 INVESTIGATIONAL PLAN

2.1 Overall Study Design

This is an evaluator-blinded study using a within-subject randomized design. Each subject will receive all investigational products at the same time. The trained skin evaluator and Investigator will be blinded to the identity of the test materials. The investigational products will be OmezaTM Collagen Matrix liquid and a negative control (0.9% aqueous sodium chloride). The study will involve repetitive and continuous patch applications of all investigational products approximately 48 hours on weekdays and for approximately 72-hour periods over weekends over 3 weeks, for a total of 9 induction applications. Sites on the back area will be evaluated by the blinded trained evaluator after each patch removal. Subjects will have a rest period of 10 – 17 days, followed by challenged applications of each investigational product to naïve sites for approximately 48 hours. Evaluations of the challenge sites will be made approximately 30 minutes, 24 (± 1), 48 (± 2) and 72 (± 2) hours post removal. Total study duration after screening will be approximately 5-6 weeks for each subject.

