The challenge patches will be applied to naïve sites on the opposite side of the back for approximately 48 hours. Challenge sites will be evaluated approximately 30 minutes, 24 (± 1), 48 (± 2) and 72 (± 2) hours after patch removal. Evaluation of the test articles for the potential to sensitize should include a review of the induction site scores as well as the challenge site scores and a narrative description of any reaction observed at challenge will be recorded. The opinion from the investigator as to whether the reaction is indicative of contact sensitization will be documented in the study records and reported in the final report.

Photos will be taken of any reactions of concern and will be shared with the sponsor but will not be part of the final report.

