7 STATISTICAL METHODS

7.1 Randomization

A computer-generated randomization scheme will be used to obtain a balanced allocation of each test code to each treatment site.

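### The protocol gives no separate allocation for the challenge patches; if the Visit 1 positions carry over, any recognition of the product site in induction reaches the decisive challenge reading

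*Combined protocol and SAP*

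**What the plan says.** **Allocation.** Section 6.5 describes the induction patches ("for a total of 9 induction applications"), places the first at Visit 1, and ends the paragraph with "All remaining patch applications will occur following the same randomization scheme as on Visit 1". The next paragraph covers the challenge and says nothing about allocation. Section 7.1 adds only "A computer-generated randomization scheme will be used to obtain a balanced allocation of each test code to each treatment site". Sections 2.2, 4.3, 4.4 and 6.7 likewise describe one assignment of codes to sites.

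**Sites.** Section 4.4 uses two induction sites on one side of the back. Under Section 6.6 the challenge patches go to naïve "sites on the opposite side of the back for approximately 48 hours". No rule links a subject's induction positions to the challenge positions.

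**Readings.** Section 2.1: "Sites on the back area will be evaluated by the blinded trained evaluator after each patch removal". Section 6.6: "The same individual will conduct all skin evaluations of the test sites, but a qualified back-up individual will be available if needed".

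**Safeguards.** Section 6.6: "The evaluator and Investigator will be blinded to treatment assignment and any previous scores". Under Section 4.4 study personnel apply and remove the patches, and staff wipe off residue before the reading if they see any.

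**Decision.** Section 6.8 takes redness with swelling at the product site during the challenge, with no reaction at the saline site, as the sign of sensitization. The Principal Investigator reviews the scores together with the grader.

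**The concern.** The outcome is a visual grade, and Section 7.2 plans no statistical analysis. Blinding is therefore a main protection for the comparison with saline, and it matters most at the challenge. Section 2.2 itself gives removal of evaluator bias as the purpose of randomizing positions.

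There are only two sites, so identifying one identifies the other. Induction offers several possible cues:

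- a site that reacts, or that is moved to adjacent skin because of excessive irritation (Sections 4.4 and 6.6);
- a lasting mark, since the scale in Section 6.6 includes hyperpigmentation, scabbing and peeling;
- residue that is not fully wiped off.

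The challenge is read on the other side of the same back, so a mark that persists could still be in view. It would then serve a back-up reader as well as the usual one. If the relative position carries over, grading at the challenge could drift towards or away from the product.

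**Working it through.** **1. Number of induction readings.** The day row of Table 5-1 is 1, 3, 5, 8, 10, 12, 15, 17, 19, 22. The successive gaps are 2, 2, 3, 2, 2, 3, 2, 2 and 3 days, which is 9 wear periods, 9 removals and 9 readings (Visits 2 to 10). This reproduces the stated 9 applications. Section 5.3 lists no application at Visit 10. The challenge adds 4 readings: about 30 minutes, then 24, 48 and 72 hours after removal.

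**2. Does the Visit 1 scheme reach the challenge?** The two readings of Section 6.5 lead to different places:

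- *Literal.* The challenge patch is a remaining application, so it follows the Visit 1 scheme.
- *By placement.* The sentence belongs to the induction paragraph, so the challenge allocation is not stated anywhere.

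The first reading carries the position over. The second leaves it open. Neither provides an independent challenge allocation.

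**3. What carry-over would do.** Let r be the share of subjects whose product position the evaluator recognised in induction. The documents give no value, so r is an assumption shown over its full range. In the other subjects the evaluator guesses, with probability 1/2.

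- Position carried over: P(correct at challenge) = r × 1 + (1 − r) × 1/2.
- Independent 1:1 challenge allocation: P(correct from induction knowledge) = r × 1/2 + (1 − r) × 1/2 = 1/2.

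The counts are for the 50 completers the protocol aims for.

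| r (assumed) | Carried over | Of 50 | Independent | Of 50 |
|---|---|---|---|---|
| 0 | 50% | 25 | 50% | 25 |
| 0.25 | 0.25 + 0.375 = 62.5% | 31.25 | 50% | 25 |
| 0.5 | 0.5 + 0.25 = 75% | 37.5 | 50% | 25 |
| 1 | 100% | 50 | 50% | 25 |

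**4. Can weak cues add up?** Suppose each reading points to the right site with probability p, independently, and the evaluator goes with the majority of 9. Then P(correct) = P(X ≥ 5) with X binomial (9, p): 73% at p = 0.6, 90% at p = 0.7 and 98% at p = 0.8. Both p and the independence are assumptions. Cues at one site are likely to be correlated, and the evaluator would have to remember them, so this is an illustration and not an estimate.

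**The case against.** The case against is substantial.

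- **Placement of the sentence.** It ends the induction paragraph. A single predetermined scheme could list different positions for induction and challenge, and Section 7.1 does not exclude the challenge sites. A reader might infer that the protocol fixes the same relative position at challenge; on the induction-only reading it is silent. This stands.
- **Recognition.** A reader might also infer that the evaluator will know the product site at challenge, and quote the 100% figure. That figure holds only if every position was recognised and carried over. At r = 0 there is no departure from chance. The documents do not show that the product is recognisable. This stands.
- **Safeguards.** Evaluator and Investigator are blinded to assignment as well as to previous scores, residue is wiped if seen, and a back-up reader is allowed, so it is not certain that one person reads everything. Carrying knowledge forward by memory means recalling positions for up to about 60 subjects across a rest of 10 to 17 days. These points lower the likely r. They do not bring it to zero: withheld score sheets do not erase memory of a site, and a moved site or lasting mark on the same back needs no memory. No section provides a check of blinding.
- **Limits of the remedy.** Cues that arise at the challenge reading itself, such as fresh residue, would remain under any allocation. This stands, so the 50% applies only to knowledge brought from induction.

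**Conclusion.** The concern holds as a gap in the design text with a cheap remedy. It is not a demonstrated loss of blinding. The protocol either carries the Visit 1 positions to the challenge or does not say how challenge positions are set, and both cases need a change of wording.

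Under carry-over, correct identification at challenge ranges from 50% to 100% of subjects, depending entirely on the assumed r. An independent allocation holds the contribution from induction at 50%. The effect on the grades themselves cannot be derived: the documents give neither a recognition rate nor any measure of how far knowing the position would shift a grade. A reader might count all 4 challenge readings in all 60 subjects as affected. That is a ceiling which needs recognition in every subject and no dropout, while the plan expects about 50 completers.

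**What to change.** In Section 6.5, limit the sentence on following the Visit 1 scheme to the remaining induction applications. In Section 7.1, add a second, independently generated and balanced allocation of codes A and B to the two challenge positions, held by the patch-application staff and not shown to the evaluator or Investigator. State that induction and challenge scores are linked by product code; the comparison in Section 6.8 then needs no fixed position.

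A separate challenge reader would be a weaker alternative: it removes memory, but not marks still visible on the back.

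The cost is one more column in the randomization list and a few words of protocol text. The downside is a slightly higher chance of a mis-applied challenge patch. The application records already required by Sections 4.2 and 6.5 control this, provided they show which code went to which position.
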